5.4 Adjustments for Covariates

Where indicated analyses will include a covariate for study stratification ‘D-dimer level at screening’ ($>$ or $\leq 2X$ the assay's ULN).

5.5 Multi-center Studies

Data from all centers will be pooled for analysis.

5.6 Pooling of Dose Groups

The primary analysis will involve a comparison of the pooled rNAPc2 treatment groups against the heparin treatment group. Because the optimal dose of rNAPc2 is unknown and its determination is a key objective of Phase 2b, the assumption that both doses will be effective and thus can be pooled for statistical analysis may not be correct. Therefore, each rNAPc2 dose regimen will also be analyzed as separate groups.

Although this variable is included as a pre-specified subgroup of interest, it is of higher inferential priority because it does not share the same characteristics of the other subgroups, attributable entirely to the fact that group membership is determined solely by the experimental manipulation (i.e., treatment assignment) rather than any subject- or clinically-derived characteristic.

5.7 Multiplicity Issues

Multiplicity control will be implemented for non-primary endpoints as described in [Gou et al \(2014\)](#), which is an improvement uniformly over the stepwise Hochberg procedure and in most cases over the Hommel procedure.

5.8 Transformations and Normality

In circumstances where univariate or multivariate normality is assumed but violated (where violations are determined via Shapiro-Wilk test), featured in the present study primarily in the Bayesian Linear Mixed Effects models, variable transformation will be performed in order to satisfy normality assumptions. Candidate transformations include square root, logarithmic, and reciprocal transformation for incremental severity of distributional skewness.

The expected circumstances where transformation may need to be applied are certain biomarkers like D-dimer.

6 Baseline Characteristics and Subject Disposition

6.1 Subject Disposition

Subject disposition will be summarized by treatment group in a table for all screened participants, and analysis population (ITT, mITT, Per Protocol) will be reflected within the table.

6.2 Demographics and Baseline Characteristics

Baseline demographic information and clinical characteristics including, but not limited to, sex, race, ethnicity, age, ACTT ordinal scale category, severity as identified by the WHO COVID severity definitions ([Appendix 14.1](#)), and study entry D-dimer value will be listed and summarized by treatment group for the ITT and Per Protocol populations and listed for all screened participants.

6.2.1 Baseline (pre-randomization) & Concomitant (post-randomization) Medications

Concomitant medications consist of any medication given during the observation window. Concomitant medications will be coded using WHODrug as described in the DMP. Medications will be listed and summarized by Anatomical Therapeutic Chemical (ATC) Class 2nd Level, medicinal product name, and treatment group. Selected relevant medication classes will be presented as shown below. Concomitant medications at screening will be listed by participant and summarized.

Selected Relevant Concomitant Medication Classes:

- Antiplatelet
 - Aspirin
 - P2Y12 inhibitor – e.g., clopidogrel, prasugrel, ticagrelor, ticlopidine
 - Other – e.g., dipyridamole; vorapaxar, cilostazol
- Anticoagulants
 - Warfarin
 - Factor Xa inhibitors (apixaban, rivaroxaban)
 - Unfractionated heparin
 - Low molecular weight heparin
- COVID therapies
 - Systemic (non-topical) corticosteroids
 - Remdesivir
 - Baricitinib
 - Tocilizumab
 - Convalescent and non-convalescent plasma
 - Monoclonal or polyclonal Abs directed against SARS-CoV-2
 - Anti-inflammatory agents
- NSAIDS

- Vasopressors
- Inotropes
- SARS-CoV-2 vaccine (Vaccine received yes or no; manufacturer, if known)

If medication start date and end date are blank, it is assumed the medication was taken concomitantly with study drug. If medication start date and end date are both prior to Day 1, the medication will be considered as taken ‘prior’ to study drug. If medication start date is prior to Day 1 and end date is blank, the medication will be considered ‘ongoing’ and as a concomitant medication.

6.2.2 Medical History

The incidence of medical/surgical history (including COVID-19 and cardiovascular specific medical history) will be listed and summarized by treatment group for the ITT and Per Protocol populations and listed for all screened participants.

6.2.3 Vital Signs

Vital Sign data will be listed and summarized by treatment group for the ITT and Per Protocol populations and listed for all screened participants.

6.2.4 Physical Examination

Vital Sign and Physical Examination data will be listed and summarized by treatment group for the ITT and Per Protocol populations and listed for all screened participants.

6.3 Treatment Exposure and Adherence

Treatment exposure and adherence will be summarized by treatment group for the ITT, Per Protocol and Safety population and listed.

7 Efficacy Analysis

The following efficacy analyses will be based on the ITT population and data scope. Accompanying analyses pertaining to mITT and Per Protocol population, subgroup and sensitivity are discussed in [Section 11](#).

7.1 Primary Efficacy Endpoint

The primary efficacy endpoint of Phase 2b is proportional change in D-dimer level from baseline (Day 1 visit where randomization occurs and central laboratory samples are drawn) to Day 8, or Day of Discharge if prior to Day 8 between treatment groups. The primary analysis will involve a comparison of the pooled rNAPc2 treatment groups against the heparin treatment group.

7.1.1 Primary Analysis of the Primary Efficacy Endpoint

Proportional change, represented by percent change, will be calculated as $100 \times (\text{D-Dimer level at Day 8 or Day of Discharge if prior to Day 8} - \text{D-Dimer level at baseline}) / \text{D-Dimer level at baseline}$ and will be based on data provided by the central laboratory, or local laboratory paired samples if the central laboratory values are not available. The pairing process will be operationalized as outlined:

For Day 1 (baseline) paired local-local or central-central laboratory values:

1. Use any lab D-dimer drawn during the current admission and up to randomization

2. Use the laboratory sample closest to randomization if there are multiple D-dimer measurements.
3. All samples obtained more than 1-hour post-initiation of study drug are ineligible.

For Day 8 or Day of Discharge paired laboratory values:

1. Use laboratory samples collected within ± 48 h of the Day 8 or Day of Discharge study visit (whichever occurs first).
2. If there are multiple laboratory samples collected within that window, use the lab value on the target day; if not available, use the lab value immediately after the target visit day.

A Wilcoxon rank sum test will be used to compare proportional change from baseline to Day 8, or Day of Discharge if prior to Day 8, between treatment groups. The between treatment group rank sum test is considered the primary analysis of the primary endpoint.

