9.4.7 SUBGROUP ANALYSES

For the primary efficacy endpoint for each Phase, the treatment effects across the following subgroup factors will be examined:

- D-dimer
- Gender
- Age group (<65, ≥65 years)
- Race/ethnicity
- Planned or ongoing therapy with an agent with demonstrated efficacy in patients with COVID-19 (yes, no)
- Baseline ACTT ordinal scale category
- Background antiplatelet therapy at baseline

For the Phase 2b primary efficacy endpoint, possible heterogeneity in the treatment effect for subgroups within each factor will be assessed by including the factor and the interaction between the factor and treatment in the analysis of covariance (ANCOVA) model.

Additionally, the heterogeneous application of heparin dichotomized by therapeutic vs. prophylactic uses, as well as the different standards of use across site, pose the need for sensitivity analyses to determine the degree to which the primary endpoint finding generalizes across sites.

Similarly, for the Phase 3 primary efficacy endpoint, possible heterogeneity in the treatment effect for subgroups within each factor will be assessed by including the factor and the interaction between the factor and treatment in the Cox proportional hazards model.

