2.2 Sample Size Determination

During Phase 2b, approximately 160 participants will be enrolled and randomized 1:1:2 to rNAPc2 dose regimen 1, rNAPc2 dose regimen 2, and heparin SoC, respectively. Assuming approximately 20% of participants may not be evaluable for any reason, 160 randomized participants will provide for approximately 130 evaluable participants. At a sample size of 160, the study will have adequate power across a range of clinically meaningful effect sizes, operationalized as proportional reductions in D-dimer (relative to heparin) from 20% to 40% in increments of 5% (see below). This sample size was selected, based on a statistical simulation using Wilcoxon rank sum and assuming a 20% missing/dropout rate, to ensure inferences for the primary endpoint analysis will be robust, given certain potential confounding factors such as missing data (random or non-random), heterogeneous application of heparin (low molecular weight and unfractionated; prophylactic and therapeutic), effects of subject-level covariates (e.g., comorbidities), and effects of site-level covariates (e.g., country).

Power, Primary Endpoint							
	Effect Size (Proportional Reduction)						
	Enrolled Subjects	Evaluable Subjects	20%	25%	30%	35%	40%
Sample Size	80	64	55.8%	67.4%	75.6%	81.0%	84.5%
	100	80	60.5%	72.7%	80.1%	84.9%	87.8%
	110	88	63.6%	76.2%	80.7%	86.6%	89.2%
	120	96	65.2%	78.0%	82.8%	86.9%	91.0%
	130	104	68.2%	79.3%	84.8%	88.7%	91.7%
	140	112	68.9%	80.7%	86.6%	89.3%	92.5%
	160	128	71.3%	83.1%	88.3%	91.3%	94.1%
	180	144	74.9%	84.5%	89.5%	92.5%	94.6%
	200	160	77.2%	86.5%	91.0%	93.8%	95.8%

*Significance via $\alpha = 0.05$
 †Simulated with 20% Missing Data
 ‡Percentages as Averages Across Other Simulation Conditions

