7.4 Significance

All statistical tests and confidence intervals will use a 2-sided analysis with a significance level of $\alpha = 0.05$.

8 Safety Analysis

The following safety analyses will be based on the Safety population and on-treatment data scope. Additional safety analyses are detailed in [Section 11.4](#).

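### The primary D-dimer test uses baseline only as a divisor and gives no effect estimate; a baseline-adjusted supportive analysis with a confidence interval would add power, by an amount the documents do not fix

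*SAP*

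**What the plan says.** SAP 7.1.1 computes percent change in D-dimer from baseline to Day 8, or to discharge if earlier. It uses central laboratory values, or local pairs where central values are unavailable. The test is "A Wilcoxon rank sum test will be used to compare proportional change from baseline to Day 8" between groups, and "The between treatment group rank sum test is considered the primary analysis of the primary endpoint". SAP 7.1 adds: "The primary analysis will involve a comparison of the pooled rNAPc2 treatment groups against the heparin treatment group".

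SAP 5.4 provides for one covariate, the two-level screening D-dimer stratum, only in analyses that call for it. Section 7.1.1 does not. SAP 7.4 sets the general rule: "All statistical tests and confidence intervals will use a 2-sided analysis with a significance level of" 0.05. Section 7.1.1 itself names no estimator or interval for the group difference.

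In SAP 2.2, "approximately 160 participants will be enrolled and randomized 1:1:2 to rNAPc2 dose regimen 1", regimen 2 and heparin. The sample size is "based on a statistical simulation using Wilcoxon rank sum and assuming a 20% missing/dropout rate". The target effects are "operationalized as proportional reductions in D-dimer (relative to heparin) from 20% to 40% in increments of 5" percentage points.

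Continuous baseline D-dimer appears as an explanatory variable only in the imputation model of SAP 11.1. The Bayesian mixed model in SAP 11.2 names the subgroups, the D-dimer stratum and site. Its description in SAP 14.2.1 is a heading without text in the public copy.

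**The concern.** Ranking percent change is the same as ranking log(Day 8) minus log(baseline), because one is a monotone function of the other. This analysis forces a slope of 1 on log baseline. If the true slope is below 1, patients with high baselines fall further for reasons unrelated to treatment, and that variation stays in the comparison as noise. A covariate would remove it without extra patients.

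Two things are at stake. One is power: the SAP's own figure for a 20% reduction at 160 patients is 71.3%. The other is the form of the answer. The design is stated as a proportional reduction relative to heparin, but the primary analysis as written gives a p-value and no estimate in those units. The second gap does not depend on r.

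**Working it through.** **Inputs from the documents.** 160 randomised 1:1:2 gives 80 against 80 after pooling the two doses. With 20% missing, 128 are evaluable, 64 per group. Two-sided alpha is 0.05. Stated power at 160 is 71.3, 83.1, 88.3, 91.3 and 94.1% for reductions of 20, 25, 30, 35 and 40%.

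**Not in the documents.** The SD of the log ratio, r, and the list of simulation conditions.

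**Step 1: the stated power.** For a reduction d, with n = 64 per group and Wilcoxon efficiency 3/π = 0.955, power = Φ(|ln(1−d)| × √(0.955 × 64/2) / SD − 1.96). Solving for the SD:
- 20%: 0.2231 × 5.528 / (1.96 + 0.562) = 0.489
- 30%: 0.3567 × 5.528 / (1.96 + 1.190) = 0.626
- 40%: 0.5108 × 5.528 / (1.96 + 1.563) = 0.801

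No single SD fits. The best one (0.505) matches 5 of the 45 cells within 2 points. The table is footnoted as an average over other simulation conditions, so this does not show it to be wrong. It does mean that the gain below can only be calibrated to the table, not derived from it.

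**Step 2: effect of baseline adjustment.** Let k be the ratio of baseline SD to Day 8 SD on the log scale. The variance after adjustment, relative to the change score, is (1 − r²) / (1 + k² − 2rk). With k = 1 this is (1 + r)/2. Holding rank efficiency fixed, adjusted power = Φ((1.96 + z) × √(2/(1 + r)) − 1.96), where z is the normal quantile of the stated power.

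Example, 20% reduction and r = 0.5: 2.522 × 1.155 − 1.96 = 0.952, and Φ(0.952) = 83.0%, a gain of 11.7 points.

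| Assumed r | Power at 20% (stated 71.3) | Gain | Power at 40% (stated 94.1) | Gain |
|---|---|---|---|---|
| 0.3 | 87.9 | 16.6 | 99.2 | 5.1 |
| 0.5 | 83.0 | 11.7 | 98.2 | 4.1 |
| 0.7 | 78.1 | 6.8 | 96.9 | 2.8 |
| 0.8 | 75.8 | 4.5 | 96.0 | 1.9 |
| 0.9 | 73.5 | 2.2 | 95.1 | 1.0 |

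**Step 3: simulation check.** 4,000 trials per cell, 64 against 64, 20% reduction, SD 0.489, k = 1:

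| r | Wilcoxon on change | Log ANCOVA | Rank test on baseline-adjusted residuals |
|---|---|---|---|
| 0.3 | 69.9 | 88.7 | 86.8 |
| 0.5 | 71.2 | 83.8 | 81.6 |
| 0.7 | 69.3 | 77.2 | 75.4 |
| 0.9 | 70.3 | 74.7 | 72.2 |

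Log ANCOVA gains a little more than Step 2 because it also leaves the rank test, and the simulated data are normal on the log scale.

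**Step 4: sensitivity to the assumptions.**
- *Unequal variances.* At r = 0.5 and k = 0.7 the variance ratio is 0.75/0.79 = 0.949, and power at a 20% reduction is 73.5%, a gain of 2.2 points. At k = 1.2 it is 0.75/1.24 = 0.605 and 90.0%, a gain of 18.7. When k = r the true slope is 1 and the gain is zero. Inclusion criterion 5 requires D-dimer above the upper limit of normal at screening. That cuts the lower tail and may push k below 1.
- *Averaging over SDs.* If the stated powers average over differing SDs, an illustrative mixture that fits the 160-patient row within 2.6 points gives gains of 1.3 to 8.3 points for r from 0.7 to 0.3 across the five effect sizes. The mixture is not unique.

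**Step 5: which adjusted test.** In the same set-up, a Quade test (Day 8 ranks adjusted for baseline ranks) gave 81.5% at r = 0.5, 74.0% at 0.7, 70.5% at 0.8 and 68.0% at 0.9. The Wilcoxon figures were 71.6, 70.4, 70.3 and 71.2% (2,000 trials per cell). Percent-change ranks adjusted for baseline ranks gave 86, 81, 76 and 73% at r = 0.3, 0.5, 0.7 and 0.9.

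**The case against.** The strongest reply is that the plan already uses baseline, the test is valid, and the size of any gain is unknown. All three parts stand. A reader might infer that the plan ignores baseline; it does not, since percent change divides by it. A reader might also infer a fixed loss of 3 to 16 points. That range needs r between 0.3 and 0.7, equal variances and a separate SD for each effect size, none of which the documents supply.

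A second reply is that changing the primary test carries risk, and this also stands. The SAP revision history records that the primary analysis wording was clarified in answer to the regulator's review. A Quade test on raw Day 8 values could lose power at high r. It would also give up the same-laboratory pairing of SAP 7.1.1, which cancels a proportional assay difference within a patient. With an assumed 20% of pairs local and shifted fourfold up or down, Quade gave 69.4% against 69.9% for Wilcoxon at r = 0.5.

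Third, related analyses exist elsewhere. Protocol 9.4.2 plans to relate effect to baseline D-dimer elevation, SAP 5.6 analyses each dose separately, and SAP 5.8 allows transformation. None visibly puts continuous baseline D-dimer into the main comparison or names an estimate for it. Whether the Bayesian model does cannot be judged from the public copy.

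Protocol 9.4.7 refers to an interaction between "the factor and treatment in the analysis of covariance (ANCOVA) model". A reader might infer that a primary ANCOVA was planned and lost. That does not follow: the sentence concerns subgroup heterogeneity, Protocol 9.4.1 lets the SAP supersede, and SAP 11.2 uses a different model.

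**Conclusion.** The point holds as one of efficiency and reporting, not validity. The primary test uses baseline D-dimer only through the ratio, adjusts for nothing, and comes with no effect estimate. Under log-normal data, equal variances and calibration to 71.3% power at a 20% reduction, baseline adjustment is worth about 7 to 17 points for r of 0.7 to 0.3 and about 2 to 5 points for r of 0.9 to 0.8. Larger effects, averaging over SDs (about 1 to 8 points) or a less variable baseline reduce this.

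A reader might also infer that the adjusted pooled estimate would choose the Phase 3 regimen. It cannot, because pooling removes the dose contrast. Only dose-specific estimates bear on that choice.

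**What to change.** Before unblinding, name as the first supportive analysis of the primary endpoint an ANCOVA of the log ratio (Day 8 or discharge over baseline) on treatment, log baseline D-dimer, screening D-dimer stratum and laboratory source (central or local). Report the ratio of geometric means with 95% CI for pooled rNAPc2 against heparin and for each dose against heparin. With log baseline in the model, the log ratio gives the same treatment effect as log Day 8 would. State the r and SD used in the power simulation.

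Keep the Wilcoxon test as primary. If the sponsor also wants an adjusted rank-based primary test, use percent-change ranks adjusted for baseline ranks, which keeps the reviewed endpoint and the same-laboratory pairing. Do not use a Quade test on raw Day 8 ranks.

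The cost is a few lines of SAP text and code, plus notice to the regulator only if the primary test changes.
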